FANC	Federal Agency for Nuclear Control
GCP	Good Clinical Practice
GDPR	General Data Protection Regulation
IB	Investigator's Brochure
IC	Informed Consent
ICF	Informed Consent Form

ICH	International Conference on Harmonisation
ICA	Invasive Coronary Angiography
IHCA	In-Hospital Cardiac Arrest
IMP	Investigational Medicinal Product
IMPD	Investigational Medicinal Product Dossier
IVUS	Intravascular Ultrasound
MCS	Mechanical Circulatory Support
MS	Member State
NSTEMI	Non-ST Elevation Myocardial Infarction
OCT	Optical Coherence Tomography
OHCA	Out-of-Hospital Cardiac Arrest
PCI	Percutaneous Coronary Intervention
PI	Principal Investigator
ROSC	Return of Spontaneous Circulation
RSI	Reference Safety Information
SAE	Serious Adverse Event
SAR	Serious Adverse Reaction
SmPC	Summary of Product Characteristics
SOP	Standard Operating Procedure
STEMI	ST Elevation Myocardial Infarction
SUSAR	Suspected Unexpected Serious Adverse Reaction
VA-ECMO	Veno-Arterial Extracorporeal Membrane Oxygenation

3 Protocol Version History

Version N°	Version Date	Summary of changes
1	March 4 th 2025	

4 Trial Registration/Protocol Summary

Information	
Objectives:	Investigate the feasibility and diagnostic accuracy of ECG-less gated CCTA in cardiac arrest survivors without STEMI, by means of agreement with ICA.
Study population:	Cardiac arrest survivors without STEMI.
In- and exclusion criteria:	
 - Inclusion: 
 o Adults (≥ 18 years) with sustained return of spontaneous circulation (ROSC) following in/out-of-hospital cardiac arrest. o Informed consent from patient or representative obtained before invasive coronary angiography. - Exclusion 
 o Patients on VA-ECMO o ACS STEMI or STEMI "equivalent" 
 ▪ New left/right bundle branch block ▪ ST segment depression in leads V1-V3, when the terminal T wave is positive and concomitant ST-segment elevation $\geq 0,5$mm recorded in leads V7-V9 (posterior MI) ▪ ST-segment elevation in V7-V9 (posterior MI) or V3R-V4R (RV MI) o ACS NSTEMI with persistent ST depression despite optimal therapy, suggesting ongoing myocardial ischemia, with indication for an urgent ICA according to the treating physician. o Hemodynamic/electrical instability precluding CT imaging (as perceived by the treating physician) o Life-threatening arrhythmia potentially caused by acute myocardial ischemia o Absolute contraindications to iodinated contrast o Patients with a known non-cardiac cause of cardiac arrest (e.g., traumatic brain injury, overt hemorrhage, asphyxia/severe hypoxia due to known lung disease, trauma, severe metabolic/electrolyte derangement, or intoxication) as perceived by the treating physician, where chest CT is considered unnecessary. o Known or likely pregnancy or lactation o Severe bleeding issue (as perceived by the treating physician) precluding heparin administration during radial access coronary angiography. o Prior coronary intervention (stent implantation/CABG). o CT findings indicating a condition that precludes coronary angiography in the short term. o Patients with end-of-life care pathways. o Participation in another intervention study interfering with the research questions in OPEN CCT Arrest.
Factors of interest / Data to be collected:	
Chest CT scan (as early as possible) + CT brain (+ CT abdomen if perceived indicated by the treating physician)
 
Pulmonary embolism/aortic dissection protocol
 
ECG-less gated CCTA
 
Invasive coronary angiography (<24 hours after CT scan)
 
Registration of baseline characteristics at admission
 
Registration of in study related parameters
 
Assessment of 90 days outcome

	Assessment of agreement between ECG-less CCTA and ICA
Endpoints:	
Primary endpoint will be the percentage of patients correctly classified to coronary artery disease as the cause of cardiac arrest after the CT scan.
 
Secondary endpoints
 
 - level of agreement between CCTA and ICA based evaluation of the degree of coronary stenosis. - Feasibility: data on coronary stenosis based on ECG-less CCTA cannot be provided or is incompletely provided. - Reasons for failure of complete CCTA reporting. - Clinical outcomes at 90 days.
Target sample size:	30 patients
Statistical considerations:	We will make use of descriptive statistics. The level of agreement will be assessed with the Weighted Kappa coefficient.

5 Background and Rationale

5.1 Overview of Relevant Literature

Acute coronary syndrome (ACS) is the most important treatable cause of cardiac arrest. In contrast with cardiac arrest survivors with ST elevation myocardial infarction (STEMI), current guidelines do not recommend unselected/routine urgent invasive coronary angiography (ICA) in the patients with cardiac arrest without STEMI¹. This recommendation reflects existing evidence indicating that immediate invasive strategies may not confer significant benefit in this population and may even be harmful^{2,3,4}, while another ongoing randomized controlled trial is investigating this⁵. Nevertheless, in COACT², a landmark trial investigating a strategy of immediate versus delayed coronary angiography in out-of-hospital cardiac arrest patients without STEMI, one or more culprit coronary lesions responsible for triggering cardiac arrest were identified in 40% of the total patient population. The question remains pertinent whether well selected cardiac arrest survivors without STEMI can benefit from early ICA. Yet, current available clinical tools fail to identify these patients. Markers such as clinical history, echocardiographic abnormalities, arrest rhythm (shockable/non-shockable), ECG changes other than ST-segment elevation and troponin levels lack sufficient sensitivity and specificity in a cardiac arrest setting for predicting ACS requiring intervention^{6,7,8,9,10,11}.

The diagnostic value of ECG-gated cardiac computed tomography angiography (CCTA) for detection of both acute and chronic coronary artery syndrome is well established^{12,13}, with recent evidence demonstrating the additional value of fractional flow reserve (FFR)-CT in ACS¹⁴. Nonetheless, the

need for ECG-gating remains a limitation.

Recently an ECG-less CCTA modality was developed, but its diagnostic accuracy is still under validation¹⁵. ECG-less cardiac or coronary CT angiography (CCTA) allows cardiac imaging without requiring an ECG signal from the patient. Thus, it eliminates the steps associated with using a patient-attached ECG monitor: skin preparation, attaching the ECG leads, checking impedance, and confirming that the leads provide an adequate ECG signal to the scanning system. Therefore, workflow is optimized, which is critical in an emergency setting. In situations where it is difficult to attach the ECG leads, such as patients in a resuscitation setting who already have diagnostic ECG leads in place or other instrumentation, it is also advantageous that there is no need for an ECG signal.

Cardiac arrest patients without STEMI and with no evident non-cardiac cause generally undergo CT imaging of head and chest for evaluation of potential causes of cardiac arrest (e.g. pulmonary embolism, acute aortic dissection, intracranial hemorrhage). While ECG-gated CCTA is considered the optimal modality for non-invasive coronary imaging, ECG-less CCTA might offer a highly interesting alternative with the advantages mentioned earlier. Other benefits include no substantially longer scanning time, no need for additional contrast injection or administration of betablockers.

In case the technique is well validated, future clinical questions could include whether ECG-less CCTA can help to identify a patient population of cardiac arrest survivors without STEMI that do benefit from early invasive coronary angiography and whether earlier treatment could improve outcome.

5.2 Study Rationale and Purpose

This study aims to investigate the feasibility and diagnostic accuracy of ECG-less gated CCTA in cardiac arrest survivors without STEMI, by means of agreement with ICA.

6 Study Objectives and Endpoints

6.1 Primary Objectives

Investigate the feasibility and diagnostic accuracy of ECG-less gated CCTA in cardiac arrest survivors without STEMI, by means of agreement with ICA.

6.2 Secondary Objectives

- level of agreement between CCTA and ICA based evaluation of the degree of coronary stenosis.
- Feasibility: data on coronary stenosis based on ECG-less CCTA cannot be provided or is incompletely provided.
- Reasons for failure of complete CCTA reporting.
- Clinical outcomes at 90 days.

6.3 Endpoints

Primary endpoint

- Percentage of patients correctly classified to coronary artery disease as the cause of cardiac arrest after the CT scan.

Secondary endpoints

- level of agreement between CCTA and ICA based evaluation of the degree of coronary stenosis.
- Feasibility: data on coronary stenosis based on ECG-less CCTA cannot be provided or is incompletely provided.
- Reasons for failure of complete CCTA reporting.
- Clinical outcomes at 90 days.

7 Research Methods

7.1 Study Design

Single-center, prospective, non randomized, interventional study.

7.2 Study Population

7.2.1 *Inclusion Criteria*

- Adults (≥ 18 years) with sustained return of spontaneous circulation (ROSC) following in/out-of-hospital cardiac arrest.
- Informed consent from patient or representative obtained before invasive coronary angiography.

7.2.2 *Exclusion Criteria*

- Patients on VA-ECMO
- ACS STEMI or STEMI "equivalent"
 - New left/right bundle branch block
 - ST segment depression in leads V1-V3, when the terminal T wave is positive and concomitant ST-segment elevation $\geq 0,5$ mm recorded in leads V7-V9 (posterior MI)
 - ST-segment elevation in V7-V9 (posterior MI) or V3R-V4R (RV MI)
- ACS NSTEMI with persistent ST depression despite optimal therapy, suggesting ongoing myocardial ischemia, with indication for an urgent ICA according to the treating physician.
- Hemodynamic/electrical instability precluding CT imaging (as perceived by the treating physician)
- Life-threatening arrhythmia potentially caused by acute myocardial ischemia
- Absolute contraindications to iodinated contrast
- Patients with a known non-cardiac cause of cardiac arrest (e.g., traumatic brain injury, overt hemorrhage, asphyxia/severe hypoxia due to known lung disease, trauma, severe

metabolic/electrolyte derangement, or intoxication) as perceived by the treating physician, where chest CT is considered unnecessary.

- Known or likely pregnancy or lactation
- Severe bleeding issue (as perceived by the treating physician) precluding heparin administration during radial access coronary angiography.
- Prior coronary intervention (stent implantation/CABG).
- CT findings indicating a condition that precludes coronary angiography in the short term.
- Patients with end-of-life care pathways.
- Participation in another intervention study interfering with the research questions in OPEN CCT Arrest.

7.2.3 *Contraception / Pregnancy Avoidance Measures*

Pregnant women will be excluded.

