Patients are scanned using a Revolution Apex Elite system (GE Healthcare, Waukesha, WI -USA). We use a hyperdrive pulmonary CT angiography (523mm/s with 0.28s/rotation gantry speed). After a short delay of a few seconds (5-12 sec), allowing the contrast to leave the pulmonary circulation, and enter the aorta and coronary arteries, a coronary CT angiography is performed within the same contrast bolus. No extra contrast is given to acquire the cardiac images. No intravenous beta-blocker nor sublingual nitroglycerin is administered. The total added exam time (assessing heart rhythm, preparing the scan parameters, the delay time and the acquisition itself) is about one to two minutes. The dose-length product (DLP) of the ECG-less cardiac scan depends on the duration of the scan time that is chosen. The average DLP is between 150 and 200 mGy.cm. The diagnostic reference level (DRL) as set by the Federal Agency for Nuclear Controle (FANC) for a coronary CT angiography is 300 mGy.cm.

The combined pulmonary CT angiography and ECG-less cardiac scan can be used to diagnose all the pathologies that can be assessed on a conventional pulmonary CT angiography scan (including, but not limited to, pneumonia, pleural fluid, pulmonary embolism, pulmonary infarct, pulmonary mass, pneumothorax, pericardial fluid, etc.) and provides extra diagnostic information about coronary artery disease.

Baseline characteristics of the study population.

Age

Sex category

BMI

Medical conditions / cardiovascular risk factors

Diabetes mellitus

Arterial hypertension

Current smoker

Dyslipidemia

Peripheral artery disease

Previous stroke / Transient Ischemic Attack (TIA)

Clinical observations during cardiorespiratory arrest

Cardiac arrest witnessed

Shockable first monitored rhythm

Bystander CPR

No flow time

Low flow time

Median time from cardiac arrest to ROSC

After hospital admission

First arterial pH

First arterial lactate level

First troponin T level

First creatinine level

Vasoactive drug(s) (Y/N)

(1) Study related parameters

- Median time from cardiac arrest to ECG-less gated CCTA
- Median time from cardiac arrest to ICA
- Catheterization access
 - o Femoral
 - o Radial
 - o Brachial
- Culprit lesion identified
- Patients with coronary artery disease without a culprit lesion
- Use of intravascular imaging (OCT/IVUS) (Y/N)
- PCI performed
- Median amount of contrast dye (CT scan)
- Median amount of contrast dye (coronary angiography)
- Total radiation dose (mSv)

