8.1.1 Screening

Screening will be performed by the treating physician in every cardiac arrest patient at the moment of ROSC.

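### Does the arrhythmia exclusion shut out the possibly ischaemic shockable arrests that the trial is meant to classify?

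*Protocol*

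**What the plan says.** The exclusion "Life-threatening arrhythmia potentially caused by acute myocardial ischemia" stands in section 7.2.2 and, identically worded, in the section 4 summary. It names no period and no assessor.

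The places that bear on how it should be read are these:

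- Inclusion (section 7.2.1) takes adults "with sustained return of spontaneous circulation (ROSC) following in/out-of-hospital cardiac arrest", with no restriction by arrest rhythm.
- Section 8.1.1 sets the time of assessment: "Screening will be performed by the treating physician in every cardiac arrest patient at the moment of ROSC".
- The primary endpoint (section 6.3) is "Percentage of patients correctly classified to coronary artery disease as the cause of cardiac arrest after the CT scan".
- Among the baseline characteristics in section 8.1 is "Shockable first monitored rhythm".
- Section 5.1 reports, from an earlier trial in out-of-hospital arrest, that "one or more culprit coronary lesions responsible for triggering cardiac arrest were identified in 40% of the total patient population". It also says that arrest rhythm and other markers, among them "ECG changes other than ST-segment elevation and troponin levels lack sufficient sensitivity and specificity in a cardiac arrest setting", do not predict well which patients have an acute coronary syndrome that needs intervention.

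**The concern.** Every candidate has just survived a cardiac arrest. A shockable arrest of possible coronary origin is, in plain words, a life-threatening arrhythmia that ischaemia may have caused. The qualifier that the cause need only be potential does little to narrow this, because section 5.1 regards the early clinical markers as poor predictors of an acute coronary syndrome needing intervention.

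If screening physicians applied the line to the index rhythm, they would turn patients away because of the very question that the trial asks. If some did and others did not, the case mix behind the percentage correctly classified would depend on who screened. Analysis could not repair this, since an excluded patient contributes no comparison of CT with invasive angiography. Other exclusions in the same list carry a limit of time, severity or judgement, and this one carries none, so the omission stands out.

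**Working it through.** **1. What the text supports.** The protocol states no figure on this point, so there is nothing to reproduce. The check is first one of reading.

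| Feature of the protocol | What it implies for the exclusion |
|---|---|
| Screening takes place at ROSC, and inclusion requires that ROSC be sustained (8.1.1, 7.2.1) | Exclusions are judged on a patient whose circulation has already returned |
| Neighbouring cardiac exclusions: VA-ECMO support, persisting ST depression with ongoing ischaemia, instability that prevents CT (7.2.2) | The group describes the patient's current state |
| The index event is called cardiac arrest, and its rhythm the arrest rhythm (5.1) or first monitored rhythm (8.1) | A separate term is used for the exclusion |
| Primary endpoint on coronary disease as the cause of the arrest (6.3) | Arrests caused by coronary disease have to be enrolled |
| Shockable first rhythm recorded at baseline (8.1) | Shockable arrests are expected in the sample |

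All five rows favour an arrhythmia that is present or recurs after ROSC. None favours the index rhythm.

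**2. Which conflicts the literal reading would create.** The described population, "cardiac arrest survivors without STEMI", is not contradicted, because exclusions narrow a population by design. The baseline variable is not contradicted either, because shockable arrests judged non-ischaemic could still enter. What remains is tension with the purpose of the primary endpoint.

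**3. How large the effect could be.** Inputs: 30 patients (section 4) and a culprit share of 0.40 (section 5.1). Assumptions not in the protocol: a fraction f of coronary-caused arrests and a fraction g of other arrests are excluded, sensitivity is 0.90 and specificity is 0.70.

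- Share after exclusion = 0.4(1−f) / [0.4(1−f) + 0.6(1−g)]
- Expected coronary-caused arrests = 30 × share
- Expected percentage correct = share × 0.90 + (1 − share) × 0.70

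| f | g | Share | Coronary-caused arrests of 30 | Percentage correct |
|---|---|---|---|---|
| equal to g | equal to f | 0.400 | 12.0 | 78.0 |
| 0.50 | 0.25 | 0.308 | 9.2 | 76.2 |
| 0.50 | 0 | 0.250 | 7.5 | 75.0 |
| 0.25 | 0.50 | 0.500 | 15.0 | 80.0 |

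The shift runs from 75.0 − 78.0 = −3.0 points to 80.0 − 78.0 = +2.0 points, so even its direction is not fixed. If sensitivity equals specificity, the share drops out of the formula and the shift is zero.

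**4. Set against sampling error.** For 23 correct of 30 (76.7%), the exact (Clopper-Pearson) 95% interval is 57.7% to 90.1%. The illustrated shifts are small beside it.

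**The case for a change.** The strongest case for a change is that intent has to be pieced together from separate sections, while a physician in an emergency applies the line as it stands. Eligibility belongs in the protocol, so a statistical analysis plan cannot settle it afterwards. The separate exclusion for electrical instability that prevents CT already covers part of the period after ROSC, so a reader may fairly ask what the arrhythmia line adds. A clarifying phrase would also cost almost nothing.

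The percentage correct may understate what is lost, too. Fewer coronary-caused arrests make any statement about sensitivity less precise. Even with every such case detected, the exact 95% lower limit is 73.5% for 12 of 12 and 63.1% for 8 of 8.

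Part of this stands. The period is not written down, and the literal reading would sit badly with the primary endpoint. But overlap with the instability exclusion does not show that the index rhythm was meant: an arrhythmia after ROSC need not prevent a CT scan, so the two lines can differ in scope without reaching back to the arrest. The loss of precision arises only if the less natural reading is applied, and to an extent that has to be assumed. That physicians at the one centre would apply the line differently is conjecture, and a reading that defeats the study's purpose is the one they are least likely to choose.

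**Conclusion.** The exclusion leaves its period unstated, and that is all that survives. Read with the time of screening, the neighbouring exclusions, the protocol's own terms and the primary endpoint, it refers most naturally to an arrhythmia present or recurring after ROSC. On that reading the trial does not exclude the patients it means to classify.

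No size can be attached from the protocol alone. The illustrated range of −3.0 to +2.0 points around 78.0% rests on assumed exclusion fractions and accuracies. It also rests on a 40% culprit share from out-of-hospital arrests, whereas this trial also enrols in-hospital arrests and excludes prior stenting or bypass surgery. The range is small beside the uncertainty of a descriptive study of 30 patients.

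The conclusion assumes that a single-centre team which knows the study question applies the line in keeping with it. A note of the intended period in the site's screening instructions would be harmless, but it would alter neither the design nor the analysis. Which arrhythmias call for another care pathway is for the investigators and is not judged here. No change to the plan is needed.

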7.3 Study Duration for Subjects

90 days.

7.4 Group Allocation & Blinding (if applicable)

Not applicable.

8 Study Assessments and Procedures

8.1 Schedule of Activities

Chest CT scan (as early as possible) + CT brain (+ CT abdomen if perceived indicated by the treating physician) Pulmonary embolism/aortic dissection protocol ECG-less gated CCTA (1)	Standard of care Study-specific
Invasive coronary angiography (<24 hours after CT scan)	Standard of care
Registration of baseline characteristics at admission (2)	Standard of care
Registration of study related parameters (3)	Study specific
Assessment of 90 days outcome (4)	Study-specific
Assessment of agreement between ECG-less CCTA and ICA (5)	Study-specific

ECG-less gated CCTA

ECG-less Cardiac software is an FDA-approved cardiac scan mode that acquires cardiac images without the need of a patient-attached ECG monitor. ECG-less Cardiac essentially utilizes existing CT system scan technology. The system uses a wide detector coverage of 160mm to provide full heart coverage and a fast gantry speed of 0.23 seconds per rotation to perform imaging in a single cardiac cycle. An estimate of the heart rhythm has to be provided, which is often readily available because emergency patients are already monitored. Based on the heart rhythm the scanner simulates an ECG signal. This simulated ECG signal provides virtual gating of the scan. The acquisition can be performed during a full heart cycle or three-quarters or half cycle, depending on how fast the heart rhythm is. The existing cardiac software options of SmartPhase (automated phase selection) and SnapShot Freeze 2 (optimized volume registration) amplify the quality of the images and correct for motion.

Patients are scanned using a Revolution Apex Elite system (GE Healthcare, Waukesha, WI -USA). We use a hyperdrive pulmonary CT angiography (523mm/s with 0.28s/rotation gantry speed). After a short delay of a few seconds (5-12 sec), allowing the contrast to leave the pulmonary circulation, and enter the aorta and coronary arteries, a coronary CT angiography is performed within the same contrast bolus. No extra contrast is given to acquire the cardiac images. No intravenous beta-blocker nor sublingual nitroglycerin is administered. The total added exam time (assessing heart rhythm, preparing the scan parameters, the delay time and the acquisition itself) is about one to two minutes. The dose-length product (DLP) of the ECG-less cardiac scan depends on the duration of the scan time that is chosen. The average DLP is between 150 and 200 mGy.cm. The diagnostic reference level (DRL) as set by the Federal Agency for Nuclear Controle (FANC) for a coronary CT angiography is 300 mGy.cm.

The combined pulmonary CT angiography and ECG-less cardiac scan can be used to diagnose all the pathologies that can be assessed on a conventional pulmonary CT angiography scan (including, but not limited to, pneumonia, pleural fluid, pulmonary embolism, pulmonary infarct, pulmonary mass, pneumothorax, pericardial fluid, etc.) and provides extra diagnostic information about coronary artery disease.

Baseline characteristics of the study population.

Age

Sex category

BMI

Medical conditions / cardiovascular risk factors

Diabetes mellitus

Arterial hypertension

Current smoker

Dyslipidemia

Peripheral artery disease

Previous stroke / Transient Ischemic Attack (TIA)

Clinical observations during cardiorespiratory arrest

Cardiac arrest witnessed

Shockable first monitored rhythm

Bystander CPR

No flow time

Low flow time

Median time from cardiac arrest to ROSC

After hospital admission

First arterial pH

First arterial lactate level

First troponin T level

First creatinine level

Vasoactive drug(s) (Y/N)

(1) Study related parameters

- Median time from cardiac arrest to ECG-less gated CCTA
- Median time from cardiac arrest to ICA
- Catheterization access
 - o Femoral
 - o Radial
 - o Brachial
- Culprit lesion identified
- Patients with coronary artery disease without a culprit lesion
- Use of intravascular imaging (OCT/IVUS) (Y/N)
- PCI performed
- Median amount of contrast dye (CT scan)
- Median amount of contrast dye (coronary angiography)
- Total radiation dose (mSv)
- Time-to-diagnosis of ACS as a cause of cardiac arrest
- Time-to-diagnosis of a non-cardiac cause of cardiac arrest
 - o Pulmonary embolism
 - o Intracranial hemorrhage
 - o Acute aortic dissection
 - o Other
- Feasibility (patients meeting inclusion criteria where ECG-less CCTA with sufficient quality was obtained)

(2) Outcome at 90 days

- Survival (Y/N)
- severe neurologic deficit (≥ 3) (Y/N)
- Median peak troponin release
- Median length of ICU stay (days)
- Median duration of catecholamine support (days)
- Median peak SAPS II score
- Rehospitalization for heart failure (Y/N)
- Acute kidney injury (Y/N)
- Need for renal replacement therapy (Y/N)
- ISTH major bleeding event
- Ischemic stroke
- Need for mechanical circulatory support (MCS)
- Treatment with Dual Antiplatelet Therapy (DAPT)
- LV function on 90 days ambulatory follow-up visit

(3) Assessment of agreement between CCTA and ICA

Degree of coronary stenosis is divided into 3 categories (0, <50%, ≥50%) for every coronary segment. Angiographic and CT images are respectively evaluated by the consensus of two interventional cardiologists (ICA) and two interventional radiologists (CCTA), blinded for clinical data. In case of discrepant results between the two readers of the same imaging modality, a third reader will provide the deciding assessment.

The level of agreement will be assessed with the Weighted Kappa coefficient.

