10.3 Database Management and Quality Control

Degree of coronary stenosis is divided into 3 categories (0, <50%, ≥50%) for every coronary segment. Angiographic and CT images are respectively evaluated by the consensus of two interventional cardiologists (ICA) and two interventional radiologists (CCTA), blinded for clinical data. In case of discrepant results between the two readers of the same imaging modality, a third reader will provide the deciding assessment.

The final conclusion on whether or not the cause of the cardiac arrest is related to the CAD, will be made by the interventional cardiologist performing the ICA, taking into account the clinical context, ECG findings, angiographic data and intracoronary imaging in case of doubt.

The level of agreement on the grade of coronary stenosis between CCTA and ICA will be assessed with the Weighted Kappa coefficient.

11 Safety Monitoring and Reporting

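### The stenosis-reading panels and the deciding third reader are masked to clinical data but not to the other modality, so the CCTA-ICA weighted kappa is open to inflation.

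*Protocol*

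**What the plan says.** Section 8.1, item (3), and section 10.3 carry the same reading rule. Each coronary segment gets one of three stenosis grades on each modality. The readers are "two interventional cardiologists (ICA) and two interventional radiologists (CCTA), blinded for clinical data". If the two readers of one modality differ, "a third reader will provide the deciding assessment". Section 10.3 then states: "The level of agreement on the grade of coronary stenosis between CCTA and ICA will be assessed with the Weighted Kappa coefficient".

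Other text that bears on how the reads are done:

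- **Order of tests.** The schedule in 8.1 puts the CT first and the ICA less than 24 hours later.
- **Use of the CT before ICA.** Section 7.2.2 excludes patients with "CT findings indicating a condition that precludes coronary angiography in the short term", so at least part of the CT is looked at and acted on before the ICA.
- **Cause of arrest.** This is a separate judgement. Under 10.3 it "will be made by the interventional cardiologist performing the ICA, taking into account the clinical context, ECG findings, angiographic data" and, in case of doubt, intracoronary imaging.
- **Setting.** Section 7.1: "Single-center, prospective, non randomized, interventional study".
- **Blinding section.** Section 7.4, headed for group allocation and blinding, reads "Not applicable".

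**The concern.** Kappa between two imaging methods describes the methods only if each is graded without knowledge of the other. A reader who knows the other result tends to move an uncertain grade toward it. The segments with most room for this are those near the 50% cut and those degraded by motion, which are also the segments where a scan without a patient ECG is most in doubt. Agreement would then be overstated where the study most needs an honest answer.

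The protocol does fix a masking rule, and fixes it twice, so this is not a detail left for an analysis plan. The rule names clinical data and omits the mask on which an agreement study chiefly depends. Agreement between CCTA and ICA is the first secondary endpoint in 6.3, and the primary objective in 6.1 is framed as agreement with ICA. Once the reads are done with the other result known, no analysis can undo it.

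**Working it through.** **Step 1: what the text permits.** The plan gives no figure to reproduce, so the first check sets the provisions side by side.

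| Question | What the protocol states |
|---|---|
| Are the panels masked to clinical data? | Yes (8.1 and 10.3) |
| Is the CCTA panel masked to ICA images, report or grades? | Not stated |
| Is the ICA panel masked to CCTA images, report or grades? | Not stated |
| Is the third reader masked to either? | No condition stated |
| When are the panel reads done relative to the other test? | Not stated |
| Can one panel grade both modalities? | No; the specialties are separate |

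*CCTA panel.* The ICA follows within 24 hours. Any CCTA panel session after that takes place when an ICA result exists.

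*ICA panel.* The CT always comes first, so its images exist whenever ICA images are graded. Timing cannot protect this panel; only masking can. Whether the coronary part of the CT is reported clinically before the ICA is not stated.

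Separate panels stop one person from scoring both tests. They do not stop a reader from seeing the other result.

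**Step 2: illustration of direction and size.** Every input here is an assumption; none is in the protocol.

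- ICA category shares (0, <50%, ≥50%): 60/25/15% or 75/15/10%.
- CCTA grade given ICA grade, independent reads, one row per ICA category. Set A: (0.85, 0.13, 0.02), (0.20, 0.60, 0.20), (0.05, 0.20, 0.75). Set B: (0.75, 0.20, 0.05), (0.25, 0.50, 0.25), (0.10, 0.25, 0.65).
- A share q of discordant segments is moved to the ICA category.
- Weighted kappa = 1 − Σ(w × observed) / Σ(w × expected), with linear weights w = |i − j|.

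Worked case: shares 60/25/15%, Set A.

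- q = 0: observed weighted disagreement = 0.078 + 2 × 0.012 + 0.050 + 0.050 + 2 × 0.0075 + 0.030 = 0.247. CCTA shares are 0.5675, 0.258 and 0.1745, so expected weighted disagreement is 0.7587. Kappa = 1 − 0.247/0.7587 = 0.674.
- q = 0.25: observed = 0.75 × 0.247 = 0.1853. CCTA shares become 0.5756, 0.2560 and 0.1684, and expected = 0.7527. Kappa = 1 − 0.1853/0.7527 = 0.754, a rise of 0.080.

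Linear weighted kappa in all four scenarios:

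| Shares, set | q = 0 | q = 0.10 | q = 0.25 | q = 0.50 |
|---|---|---|---|---|
| 60/25/15, A | 0.674 | 0.706 | 0.754 | 0.835 |
| 60/25/15, B | 0.521 | 0.566 | 0.636 | 0.754 |
| 75/15/10, A | 0.643 | 0.676 | 0.726 | 0.813 |
| 75/15/10, B | 0.475 | 0.520 | 0.590 | 0.715 |

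The rise is about 0.03 to 0.05 at q = 0.10, 0.08 to 0.12 at q = 0.25, and 0.16 to 0.24 at q = 0.50. With quadratic weights the rise at q = 0.25 is about 0.06 to 0.10 (0.749 to 0.810 at the low end, 0.555 to 0.655 at the high end). The upward direction is built in, because segments are moved only toward the other result.

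**The case against.** **Clinical data may already cover the other test.** The other test's report is part of the patient record, and section 8.1.2 uses similar language for what is drawn from the hospital's clinical data system. This reading is possible, and the wording is better called ambiguous than an admission that readers are unmasked. But neither section says so, and nothing is said for the third reader. If it is what the sponsor means, one clause settles it.

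**Stronger conclusions that a reader might infer, and that the documents do not support:**

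- *That the ICA operator or the acute CT reporter sits on the panel.* No text puts either there. Section 10.3 describes the operator's judgement of cause separately from the masked panels, and a reader who knew the clinical picture would already breach the stated mask. All that can be said is that neither person is expressly excluded in a single-centre study.
- *That section 7.4 contradicts the reader masking.* In a non-randomised study with no allocated groups, its entry is fair, and it does not cancel what 8.1 and 10.3 say.
- *That any lapse in masking biases kappa upward.* The upward expectation applies to knowledge of the other modality. Knowledge of the clinical picture alone could move agreement either way. An acute CT read made before the ICA cannot be informed by it.
- *That the kappa will be an informed re-read.* The text permits this; it does not show that it will happen.

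**Weight.** Kappa is a secondary endpoint in a 30-patient descriptive study, and reading order or export procedures usually sit in a reading manual. That limits the weight of the point but does not remove it, because the scope of the masking is stated in the protocol itself.

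**Conclusion.** The point holds in a limited form. The reader masking in 8.1 and 10.3 omits the other modality, sets no condition for the third reader, and leaves the timing of the reads open. Following it to the letter allows each modality to be graded with the other's result known, which would be expected to inflate the per-segment weighted kappa. The size cannot be derived from the documents. The figures above show only that modest carry-over could shift kappa visibly, and they rest on assumed category shares, misclassification rates and carry-over. The conclusion also assumes that clinical data is read in its ordinary, narrower sense. It concerns the panel grades only, not the operator's judgement of the cause of arrest. The text should be amended before panel reading starts.

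**What to change.** In 8.1, item (3), and in 10.3, replace the present masking clause with: *blinded to clinical data and to all images, reports and readings of the other modality*. State that this applies to the third reader too. Add that each panel's grades are locked before the other modality's results are disclosed to it.

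Where the reader pool allows, a patient's ICA operator or acute CT reporter should not read that patient for the panel. This should not be an absolute rule: the plan names two readers and one deciding reader per modality, so if the recused person is one of those three, two remain (3 − 1 = 2) and there is no tie-breaker unless a substitute is found.

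Section 7.4 needs no correction; a cross-reference to the reader masking is optional.

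The cost is the wording, the anonymised export of at most 30 × 2 = 60 image sets, and the scheduling of reads. Patient care does not change.
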